8.6 Pharmacodynamics

Pharmacodynamics biomarkers are described in Section 8.8.1.

8.7 Genetics

Pharmacogenetic analyses except whole genome sequencing will be part of the biomarker investigations in this study. See Section 8.8 for details.

8.8 Biomarkers

Biomarker investigations in the current study will include pharmacodynamic biomarker assessments and assessments of biomarkers that may associate with efficacy and/or safety.

Both genetic as well as non-genetic biomarkers will be investigated. Genetic investigations may be of any kind (including whole exome sequencing), except for whole genome sequencing.

Timing: See the SoA (Table 1–1) and the schedule of biomarker blood sampling (Table 1–2) for planned time points of sample collection.

Additional samples may be collected at additional time points during the study if warranted and agreed upon between the investigator and the sponsor. Sampling time points might also be moved or removed.

For details regarding tumor tissue collection, refer to the below specification:

Tumor tissue requirement: Formalin-fixed paraffin-embedded block (preferred) or minimum of 20 slides, obtained from core biopsy or surgical specimen.

At screening:

- Archival tumor tissue sample is mandatory if available.
- Recent tumor tissue as defined below is mandatory for all participants. Exceptions will
 be accepted for participants with no recent baseline tumor tissues after documented
 discussion and approval by the sponsor.
 - o an archival biopsy no older than 6 months and after the last anti-tumor treatment
 - o or a new biopsy.

On treatment / at EoT

- New tumor biopsies at W6D1 (+/-3 days) is mandatory if medically feasible, in consultation with the sponsor.
- Collection of a new biopsy at EoT (+ 7 days) is optional.

Page 91 of 141

Sample handling and storage: Details on the collection, processing, shipment, and storage of samples will be provided in separate documents (e.g., sample handling sheets or lab manual). Samples may be stored for a maximum of 15 years (or according to local regulations) following the end of the study at a facility selected by the sponsor to enable further analyses.

Reporting: Results of biomarker investigations may be reported separately (e.g., in a biomarker evaluation report).

8.8.1 Pharmacodynamics Biomarkers

Pharmacodynamics biomarkers will be evaluated in biomarker samples collected before and during treatment to investigate the impact of regorafenib and pembrolizumab on these biomarkers, and may be correlated with safety and/or efficacy. Tissue-based pharmacodynamics biomarker evaluations will be conducted in available paired tumor tissues (recent tumor tissues and on-treatment/EoT tumor biopsy).

Candidate pharmacodynamics biomarkers may include (but are not limited to):

- Intra-tumor pharmacodynamics biomarkers such as immune cell infiltrations (e.g. Teff, Treg, macrophages), expression of immune genes/signatures (e.g. myeloid expression signature, Treg signature), and/or parameters in the regorafenib targeted pathways (e.g. VEGFR2) in paired tumor biopsies (pre- and on-treatment)
- Quantification and characterization of immune cell populations in blood (e.g. Teff, Treg, macrophages, myeloid-derived suppressor cells [MDSC], etc.), analyzed e.g., by flow-cytometry
- Systemic levels of immune mediators (e.g., cytokines, chemokines) from serum or plasma and tumor markers from circulating tumor deoxyribonucleic acid (ctDNA)
- Plasma proteins of interest for regorafenib (e.g., sVEGFR2, angiopoietin 1 [Ang1])
- Circulating miRNA

8.8.2 Biomarkers that May Associate with Response

Baseline candidate biomarkers from tumor and blood samples will be evaluated for correlation with response to treatment (to identify possible "predictive biomarkers"). Samples from tumor materials and blood will retrospectively be analyzed.

Candidate biomarkers from baseline samples that may associate with response may include (but are not limited to):

- Tumor immune status (e.g., myeloid expression signature, Treg signature, PD-L1 expression) at baseline
- Expression of parameters of interest for regorafenib (e.g. VEGFR2) in baseline tumor materials
- Baseline TMB/tumor mutations (e.g. mutations in Wnt pathway) as detected in tumor and/or ctDNA
- Baseline immune cell populations in blood and baseline systemic levels of immune mediators (e.g., cytokines/chemokines)
- Germline genetic variants in genes of interest (e.g., cc-chemokine ligands CCL4 and CCL3, cc-chemokine receptor 5 [CCR5])
- Baseline circulating miRNA markers

Page 92 of 141

8.8.3 Other Biomarkers

In addition to the biomarkers described above, further biomarkers related to the mode of action or the safety of regorafenib and pembrolizumab and similar drugs may be examined. The same applies to further biomarkers deemed relevant to cancer and associated health problems. These investigations may include e.g., diagnostic testing, potentially predictive, safety, pharmacodynamics or monitoring biomarkers.

8.9 Immunogenicity Assessments

Blood (serum) samples will be collected from all participants treated with pembrolizumab for analysis of anti-drug antibodies (ADAs) as specified in Table 1–3. Additional exploratory ADA samples will be collected as specified in Table 1–3, which may be used for exploratory analyses including assessing the potential impact of ADAs formed against previous PD-1/PD-L1 treatment.

A decision to analyze the immunogenicity samples described above will be made during the course of the study. Until that time, samples will be stored at a central laboratory.

Instructions for the collection, processing, storage and shipment of immunogenicity samples will be provided separately by the sponsor (e.g., sample handling sheets or laboratory manual).

8.10 Medical Resource Utilization and Health Economics

Not applicable.

9. Statistical Considerations

This is a single arm, Phase 2 study with ORR per RECIST1.1 by central review as the primary endpoint.

In the pilot phase of the study, the participant population for the expansion phase is determined. Participants from the pilot phase who match the population of the expansion phase (atezolizumab plus bevacizumab vs. atezolizumab plus bevacizumab and other first line treatments) will be included in the analysis of the expansion phase.

Historical (background) response rate is assumed to be 20% (per RECIST 1.1, an ORR of 7% was observed in the regorafenib arm of the HCC trial RESORCE (Bruix et al. 2017), and an ORR of 18% was observed in the pembrolizumab arm of the HCC trial KEYNOTE-240 (Finn et al. 2020); as the sum of the ORR was about 25%, in order to show a synergistic effect this study is designed to rule out an ORR of 20%). Target response rate (i.e. true underlying response rate for which there is 95% power conditional on a positive pilot phase) will be 35%.

In addition to the number of responders, totality of data including tumor dynamics response (depth, durability) and overall safety data will be considered to make a determination to move forward to the expansion phase.

A one-sided exact binomial test with a type-I error of 2.5% will be conducted at the end of the expansion phase to test the hypothesis.

Page 93 of 141

9.1 Statistical Hypotheses

There will be no statistical hypothesis testing done in the pilot phase of the study.

The primary hypotheses to be tested in the expansion phase of the study is

H₀: ORR_{Combination} \leq 20% vs. H₁: ORR_{Combination} \geq 20%

The primary hypothesis will be tested by an exact binomial test. The significance level will be a 1-sided alpha of 2.5%.

9.2 Sample Size Determination

It is expected that approximately 170 participants will be screened to achieve the 119 evaluable participants for both study phases combined.

Pilot phase: A total of approximately 52 participants will be enrolled to receive regorafenib in combination with pembrolizumab divided in two cohorts: 26 of them after atezolizumab plus bevacizumab treatment combination (cohort 1); and 26 after any IO containing first line treatment (cohort 2), excluding atezolimab plus bevacizumab treatment combination.

Expansion phase: 2 scenarios should be considered depending on the pilot phase results.

- **Scenario 1**: if in the pilot phase at least 8 responders out of the 26 treated in cohort 1 are observed
- Scenario 2: if in the pilot phase at least 8 responders in each cohort are observed

In scenario 1, the study can continue to accrue 67 new additional participants after atezolizumab in combination with bevacizumab (i.e. a total of 93 participants after prior treatment with atezolizumab in combination with bevacizumab will be enrolled, representing the patient population of cohort 1). If 27 or more participants respond out of 93 evaluable participants (i.e. ORR 29%), the study will have ruled out an ORR \leq 20% (with 1-sided alpha of 0.025), using an exact binomial test.

In scenario 2, the study can continue to accrue 67 new additional participants after any immune checkpoint inhibitor as defined in the pilot phase (i.e. a total of 119 participants will be enrolled, representing the patient population of cohort 1 and cohort 2). If 34 or more participants respond out of 119 evaluable participants (i.e. ORR 29%), the study will have ruled out an ORR \leq 20% (with 1-sided alpha of 0.025), using an exact binomial test.

In case cohort 2 meets the response rate criterion and cohort 1 does not, the future direction for further evaluation in the expansion phase will be decided based on the totality of data and treatment landscape at the time.

If the true underlying response rate is 35%, given that at least 8 responders are observed in stage 1, the conditional power for the final analysis is at least 95%, under both scenarios above.

Page 94 of 141

9.3 Populations for Analyses

The populations for analyses are defined in Table 9–1.

Table 9-1: Populations for Analyses

Population	Description
Enrolled	All participants who sign the ICF
Full Analysis Set	All participants who take at least 1 dose of study intervention will be included in the efficacy and safety evaluation

ICF = Informed consent form

All analyses will be performed on the Full Analysis Set.

9.4 Statistical Analyses

Analyses will be performed using SAS (SAS Institute, Cary, North Carolina, USA), Version 9.2 or higher. The specific version used will be mentioned in the statistical analysis plan (SAP).

This section is a summary of the planned statistical analyses of the most important endpoints including primary and secondary endpoints. The SAP will be finalized prior to first patient first visit (FPFV) and it will include a more technical and detailed description of the statistical analyses described in this section.

9.4.1 Efficacy Analyses

9.4.1.1 General Considerations

All analyses will be conducted at one-sided type-I error level of 2.5% or two-sided type-I error level of 5% respectively. A one-sided exact binomial test will be conducted in the expansion phase to analyze the primary endpoint. Confidence intervals will be presented for selected variables.

9.4.1.2 Primary Efficacy Endpoint

The primary endpoint of the study is ORR based on RECIST 1.1 assessed by central review. ORR is defined as the proportion of participants with best overall response of confirmed CR or PR. Participants for whom best overall tumor response is not CR or PR, as well as participants without any post-baseline tumor assessment will be considered non-responders.

In both study phases, the primary efficacy variable will be analyzed after all participants are available for efficacy. The analysis will be done on the Full Analysis Set. In the pilot phase, the analysis will be done by cohort. In the expansion phase, the analysis will be done on the participants who received the first line treatment determined in the pilot phase of the study.

Methods used will include frequency tables (with the ORR table also including all "Best overall response" categories) as well as 95% two-sided Clopper-Pearson confidence intervals and the results of an exact binomial test.

9.4.1.3 Secondary Efficacy Endpoints

The secondary efficacy endpoints in this study are DOR as per RECIST 1.1 by investigator assessment and central review and ORR as per RECIST 1.1 by investigator assessment.

DOR (for PR and CR) is defined as the time (in days) from the first documented objective response of PR or CR, whichever is noted earlier, to disease progression or death (if death

Page 95 of 141

occurs before progression is documented). DOR will be defined for responders only, i.e. participants with a CR or PR. The actual dates the tumor scans were performed will be used for this calculation. DOR for participants who have not progressed or died at the time of analysis will be censored at the date of their last tumor evaluation.

The analysis will be done on the Full Analysis Set. In the pilot phase, the analysis will be done by cohort. In the expansion phase, the analysis will be done on participants who received the first line treatment determined in the pilot phase of the study.

For analyses of the secondary endpoints, proportion-based efficacy variables will be using frequency tables as well as 95% two-sided Clopper-Pearson confidence intervals. With regard to time to event data, these will be summarized descriptively using Kaplan Meier methodology and plots, as well as median estimates based on Greenwood's formula, including 95% two-sided confidence interval.

9.4.1.4 Tertiary/Exploratory Endpoints

All other endpoints will be analyzed by means of descriptive statistics using frequency tables for response endpoints and summary statistics for continuous endpoints. Further analyses will be described in the SAP.

9.4.2 Safety Analyses

All safety analyses will be done on the Full Analysis Set. In the pilot phase, the analysis will be done by first line treatment (atezolizumab plus bevacizumab vs. other first line treatments).

In the expansion phase, the analyses will be done on participants who received the first line treatment determined in the pilot phase of the study.

The incidence of TEAEs (new or worsening from baseline) will be summarized by system organ class and preferred term, severity (based on CTCAE grades), type of AE, and relation to study treatment. Deaths reportable as SAEs and non-fatal serious AEs will be listed by participant and tabulated by type of AE. AEs leading to study intervention withdrawal and/or modifications will be summarized.

Laboratory abnormalities will be summarized by severity. Frequency and incidence rates will be provided. Frequency tables will also be provided for changes in severity from baseline to worst value post-baseline. The following summaries will be generated separately for hematology and biochemistry:

- Worst change from baseline of abnormal hematological and biochemical laboratory values during treatment period
- Incidence of abnormal hematological and biochemical laboratory values during the treatment period

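### If only cohort 1 passes the pilot, Protocol 9.4.2 leaves the 26 cohort 2 participants out of the only safety analysis it names after the pilot phase

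*Protocol*

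**What the plan says.** **General rule.** Protocol 9.4.2 opens with "All safety analyses will be done on the Full Analysis Set". Table 9-1 in Section 9.3 describes that set: "All participants who take at least 1 dose of study intervention will be included in the efficacy and safety evaluation". It sets no condition on cohort or prior therapy. Section 9.3 then adds "All analyses will be performed on the Full Analysis Set".

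**Rule by phase.** Section 9.4.2 continues: "In the pilot phase, the analysis will be done by first line treatment". For the expansion phase, "the analyses will be done on participants who received the first line treatment determined in the pilot phase". Section 9 carries forward only "Participants from the pilot phase who match the population of the expansion phase". Sections 9.4.1.2 and 9.4.1.3 use the same restriction for response rate and duration of response.

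**Scenarios (Section 9.2).** Scenario 1 needs at least 8 responders among the 26 in cohort 1 and leads to 93 participants, all previously treated with atezolizumab plus bevacizumab. Scenario 2 needs at least 8 in each cohort and leads to 119.

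**SAP v3.0.** Section 5.4.1.2 lists the adverse event, serious adverse event and death outputs without mentioning a first-line restriction. Section 4 (analysis sets) refers to SAP v2.0. Appendix 2, on changes to protocol-planned analyses, is marked not applicable. The version history records that recruitment stopped early.

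**The concern.** Restricting the response-rate test to the selected population is sensible, because the hypothesis concerns that population. Safety is a different question. The safety objective in Table 3-1 concerns the combination, and both cohorts receive the same two drugs on the same schedule. Under 9.4.2, whether a cohort's later safety data reach the expansion-phase tables depends on how many responders that cohort had.

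In scenario 1 the protocol names no safety analysis after the pilot that includes cohort 2, and none that pools all treated participants. Cohort 2 participants still on treatment at the pilot analysis continue to accrue exposure. Later events among them would be collected, but the protocol assigns them to no summary table.

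**Working it through.** **1. The plan's head counts.** Inputs are 26 per pilot cohort and 67 new participants (Sections 4.1 and 9.2), and about 119 treated (Synopsis).
- Scenario 1 expansion population: 26 + 67 = 93.
- All treated: 26 + 26 + 67 = 119.

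Both agree with the plan.

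**2. Participants outside the expansion-phase safety analysis.**
- Scenario 1: 119 − 93 = 26. 26/119 = 21.8% are omitted and 93/119 = 78.2% are covered.
- Scenario 2: 119 of 119 are covered, so there is no effect.

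Section 4.2 expects no recruitment pause until interim results are available. Participants with other first-line treatment could therefore be enrolled in that interval, and in scenario 1 they too would be outside the expansion-phase analysis. On the planned numbers, 26 is then a minimum.

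**3. How readily the case could arise under the design.** It needs at least 8 of 26 responders in cohort 1 and fewer than 8 of 26 in cohort 2. With independent cohorts, the exact binomial chance of at least 8 of 26 is 0.740 at a true rate of 35% and 0.131 at 20%.

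| True rate, cohort 1 / cohort 2 | Chance |
|---|---|
| 35% / 35% | 0.740 × (1 − 0.740) = 0.192 |
| 35% / 20% | 0.740 × (1 − 0.131) = 0.643 |
| 20% / 20% | 0.131 × (1 − 0.131) = 0.114 |

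These are chances of the responder counts only. Section 9 also lets other data bear on the decision to expand.

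**4. What the pilot analysis already shows.** Cohort 2 is tabulated there, so its earlier events are reported. The protocol does not state a data cut-off for that safety analysis. If it is the interim of Section 9.5 (an assumption), it falls about 14 weeks after the last pilot participant's first dose, and later for those who enrolled earlier. Section 6.6.1 gives a median onset of immune-related colitis of 3.5 months: 3.5 × (365.25/12)/7 = 15.2 weeks. Section 6.6.3 says immune-related events can occur several months after the last pembrolizumab dose. Events after such a cut are therefore plausible.

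**5. Upper limit on the loss of information.** The chance of seeing at least one case of an event with a true rate of 1% is 1 − 0.99^n: 60.7% with n = 93 and 69.8% with n = 119. With no cases seen, the one-sided 95% upper bound on the rate is 1 − 0.05^(1/n): 3.2% with n = 93 and 2.5% with n = 119. These comparisons apply in full only to events first seen after the pilot cut, because earlier cohort 2 events are in the pilot tables.

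**6. Whether the SAP settles it.** The safety tables in SAP v3.0 carry no restriction, which points towards all treated participants. Who counts in them depends on SAP v2.0, which is not supplied, and Appendix 2 declares no change from the protocol. The supplied text does not resolve the question.

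**The case against.** The strongest reply is that 9.4.2 describes presentation by phase within the Full Analysis Set and does not redefine it. Cohort 2 enters the safety evaluation through the pilot analysis, so Table 9-1 taken alone is arguably met. The same pattern appears in the efficacy sections. Adverse event collection under Section 8.3.1 is identical for everyone, so no data are discarded. The visible SAP tables are unrestricted, and the early stop may make the matter moot. All of this stands, and it limits the point. It does not remove it: 9.4.2 puts all safety analyses on the Full Analysis Set and then defines one that omits part of that set, with no companion analysis.

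A reader might infer more than the documents support:
- **That cohort 2 safety goes unreported, or that most of its exposure does.** The pilot analysis reports it. The 14 weeks is an efficacy evaluability criterion, and no safety cut-off is given. A very long untabulated period would also need a participant who completes all 18 infusions. Section 2.2.1 cites a median treatment duration of 4.2 months for second-line pembrolizumab alone.
- **That pilot reporting by cohort hides events.** Both cohorts are shown, so an event in either appears. The amendment summary gives reporting by first-line treatment, without an overall column, as a deliberate choice to describe each population. The statement in Section 9 that "totality of data including tumor dynamics response (depth, durability) and overall safety data will be considered" does not promise a pooled table.
- **That participants are excluded for their own outcomes.** The exclusion is by prior therapy, triggered by the cohort's responder count.

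**Conclusion.** The point holds as a conditional gap in the protocol. If scenario 1 arises with cohort 2 short of 8 responders, the only safety analysis named after the pilot covers 93 of 119 planned treated participants and leaves out 26 (21.8%), plus any such participants enrolled while the interim is pending. At risk are cohort 2 events after the pilot analysis and a pooled safety table for the combination.

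This rests on planned numbers, on reading the expansion-phase sentence literally, and, for the timing, on an assumed cut-off at the interim. The documents do not show that scenario 1 arose, or that the final tables were in fact restricted; SAP v2.0 would be needed to tell. The efficacy restriction is sound and is not in question. The change is worth making because the text is inconsistent and cheap to repair.

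**What to change.** Replace the expansion-phase sentence in Protocol 9.4.2 with:

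> At the final analysis all safety outputs include every treated participant (Full Analysis Set), by first-line treatment cohort and in total.

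Keep the selected-population restriction for the efficacy analyses in 9.4.1 only. State the same population in the SAP directly, not only by reference to SAP v2.0. If SAP v2.0 already puts all treated participants in the final safety tables, record that in Appendix 2 of SAP v3.0 as a departure from 9.4.2.

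The cost is one sentence in each document and extra table columns. No new data are needed. The response-rate test is untouched: 27 of 93 keeps its exact one-sided level of 0.0238. Pilot reporting by cohort can stay as it is.

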9.4.3 Other Analyses

PK and biomarker exploratory analyses will be performed and described in separate reports.

9.5 Interim Analyses

An interim analysis will be performed to determine the participant population (participants after treatment with atezolizumab in combination with bevacizumab, or after any first line treatment) for the expansion phase of the study.

Page 96 of 141

Both cohorts from the pilot phase will continue to be expanded until a sample size of 26 evaluable participants per cohort is reached. Participants are considered evaluable for efficacy when:

- they have completed at least two post-baseline scans; or
- they have been followed for approximately 14 weeks from the first study intervention dose; or
- they have discontinued due to progression or any other reason before 14 weeks from the first study intervention dose.

The interim analysis is planned when the last participant enrolled in each of the cohorts from the pilot phase has reached the evaluation criteria outlined above. The interim analysis will be conducted on the Full Analysis Set. Both cohorts will be analyzed separately.

For this futility analysis, no formal adjustment of the type-I error will be performed.

